Title: The Outcome of Sports Vision Training on Collegiate
Softball Players

NCT number: Not assigned.

Protocol ID: 2022-1225-EXP

Date: 04 Aug 2023

Protocol for Softball Study:

Goals to address in vision training: increase eye hand coordination, peripheral awareness, visualization, concentration, depth perception, anticipation, contrast sensitivity, target accuracy, and decrease reaction time.

There are 23 ladies on the softball team. There is an eight week vision training protocol developed, not including the pre-evaluation and post evaluations, wash out and final evaluation. The training will be a required once per week 45 minute training session. They will have signups for 2 per hour so we can ensure high quality training, with strict adherence to the protocol.

There are eight tasks for each session. It was recommended to change the order of the task each week to account for order effects. So I have different training sheets for each week stapled to their others for continuity. The week one training sheets are in the Softball Folder. Please be diligent in keeping track of time, as to not go over time. You must follow the specific order of activities each week. If a conflict arises, then please make a note on which activities were completed out of order.

I have timed the protocol to be 38 minutes when I walked through it so that leaves a few minutes for changing areas etc.

No one is allowed to engage with the study participants unless they have given me their CITI training, this includes the Optometry students. If in doubt do not engage with the participants.

Most of the activity's difficulty can be adjusted to be MORE difficult for progression. They cannot be made easier than the base protocol though, so please do NOT make any activity easier. If you run out of time to complete a task just note it.

General Coaching Guidelines:

1. Always use positive reinforcement. Patients should always be verbally rewarded for good effort. If a patient is unsuccessful at the required task, the therapist should encourage the patient and commend his hard work.
2. Always ask patient how their eyes feel and how they are doing throughout each task. The therapist should try to establish an awareness on the part of the patient of what they are doing to keep the targets clear, single, and visible as they accomplish the task. The therapist should encourage the patient to keep the eyes working together and keep the targets clear throughout each activity.

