 - iii. Option Level 3: two different color balls used, subject catches the ball based on the pre-announced catching style for each color. Balls tossed from the air or bounced from the ground, athlete must try to catch the red ball in a high-hand way and the green ball in a low-hand way (colors may vary, just choose two different color balls that athlete must distinguish for either a high- or low- catch). Cannot advance to next strobe goggle level until successfully catching 6 with glove hand only
 - iv. Option Level 4: duplicate levels 1-3, with two balls and catching with both hands simultaneously. Cannot advance to next strobe goggle level until successfully catching 6 consecutive balls

-Eye Metrix Double Eye speed scanning timed 3 minutes

I will be re-arranging the eye metrix board weekly.

Be mindful of head movement, use just your eyes. Give them a laser pointer to follow along and ensure accuracy. They should use scanning techniques and grouping. Use the two number boards, this will be timed so they will start for example at 50 and work their way down, finding as many numbers as possible while alternating boards for the even and odd numbers, or every other number switch to the other board. Record what number they make it down to. If they are able to find all 50 numbers before 3:00 is done, then instruct them to start over at 50 and work their way back down and then record the total number of numbers found (50-1, 50-42)

-Synchrony

Using the synchrony light rail and the cell phone. There will be four tasks, they will do each task twice. They are titled "SB Research Inbound", "SB Research Outbound", "SB Research SLOW Inbound", "SB Research Go/ No go". The participants will "step in" and "step out" of the "batting box" for each task trial, this is to simulate their batting procedures. Have the participant stand in their batting stance in

orientation to the light rail. Use the hand held trigger. Record the Average Error and the Smallest Error of the best of the two trials.

Inbound: This is a timing task, the red/green flashing light will travel towards you at a high rate of speed (10-20mph variable) while green. You will anticipate when the green light is going to reach the white light target that is close to you, and respond with the trigger when the light is aligned with the target.

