Title: The Outcome of Sports Vision Training on Collegiate
Softball Players

NCT number: Not assigned.

Protocol ID: 2022-1225-EXP

Date: 04 Aug 2023

Research statistical analysis plan.

This is a within-subject before-after design to assess the efficacy of sports vision training on functional visual skills. Parametric repeated measures ANOVA will be used with post-hoc t-tests corrected for multiple comparisons. After completion 2 main outcomes will be evaluated: 1) a Senaptec Sensory re-evaluation will be performed to compare visual skill performance to the baseline evaluation. Results are compared to other Division 1 softball athletes in Senaptec's database and percentiles are given for each individual athlete for each skill evaluated. 2) a comparison of baseline training performance to post training performance in sports vision training activities, such as Dynavision and Senaptec Sensory Trainer activities. To analyze change in training performance, a student's T-test will be utilized to measure effect size and look for statistical significance. Analysis will utilize both individual and team comparisons. We will evaluate the impact of the sports vision program by comparing baseline values to final values for each primary outcome measure. A recommendation from literature review that we will heed, is suggesting we need to adjust the significance level, to account for multiple tests being performed, the multiple comparison correction so that statistics are not artificially inflated to significance when they are truly not.

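### If the Eye Metrix score is analysed, weekly re-arrangement of the board makes layout difficulty inseparable from change over time; counterbalance two charted layouts at the scored sessions

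*Protocol*

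**What the plan says.** In the protocol's task descriptions, under Eye Metrix Double Eye speed scanning, the study lead writes: "I will be re-arranging the eye metrix board weekly". The task is to find numbers in descending order, alternating between two boards, for three minutes. Staff are told: "Record what number they make it down to". An athlete who finishes all 50 starts again, and the total found is recorded.

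The protocol's opening section gives the setting: "There are 23 ladies on the softball team", and "The training will be a required once per week 45 minute training session". It adds: "There is an eight week vision training protocol developed, not including the pre-evaluation and post evaluations, wash out and final evaluation". Task order changes each week to deal with order effects. Neither document says whether layouts are matched for difficulty, recorded, varied between athletes or repeated, or which layout, if any, is used at the evaluations.

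The SAP states: "This is a within-subject before-after design to assess the efficacy of sports vision training on functional visual skills". Its second main outcome is "a comparison of baseline training performance to post training performance in sports vision training activities, such as Dynavision and Senaptec Sensory Trainer activities", tested with a Student's t-test. A repeated measures ANOVA is also planned, with a multiplicity correction whose method is not named. The programme is to be judged by "comparing baseline values to final values for each primary outcome measure". No layout term appears, and Eye Metrix is not mentioned.

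**The concern.** The Eye Metrix score counts numbers located on the boards in a fixed time, so where the numbers sit is part of the task. If every athlete sees one layout at baseline and another at the end, a difference in difficulty moves all the scores in the same direction. A within-athlete comparison removes stable differences between athletes, but not a shift common to all of them. A larger team would not help, because the shift does not average out. There is no concurrent control group to show it, and changing the task order deals with a different nuisance.

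An easier final layout could therefore produce a significant improvement without any training effect, and a harder one could hide a real gain.

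**Working it through.** **Inputs from the documents.** 23 athletes; 8 training weeks; one session a week; a single-group before-after design; no layout term. The documents give no alpha, effect size, SD or sample-size calculation, so there is no planned figure to reproduce.

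**Assumptions.** One layout per week for all athletes; a paired t-test, two-sided at 5%; no dropout; normally distributed changes; the layout shifts used below.

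**Step 1: can layout be separated from week?** Take a model with athlete, week and layout effects over the eight training weeks.
- Columns: 23 + 7 + 7 = 37.
- With one shared layout per week, each layout column equals a week column. The rank is 23 + 7 = 30, the same as with no layout effects. All 7 layout contrasts are aliased with the 7 week contrasts.
- If layouts are rotated across athletes, the rank is 37 of 37 and the two can be separated.

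**Step 2: what does the before-after test estimate?** For athlete i, change = δ + (L_final − L_base) + e_i, where δ is the true average change and L is the effect of the layout. The mean change estimates δ + (L_final − L_base) whatever the number of athletes.

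**Step 3: false rejection when δ = 0.** Let d be the layout shift divided by the SD of the change score. The t statistic is noncentral t with 22 degrees of freedom and noncentrality d√23. The critical value is 2.074 at 5%. With an illustrative Bonferroni split over the eight tasks, alpha is 0.05/8 = 0.00625 and the critical value is 3.023.

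| Assumed d | d√23 | Unadjusted 5% | Bonferroni, 8 tests (nominal 0.6%) |
|---|---|---|---|
| 0.2 | 0.959 | 15% | 3% |
| 0.3 | 1.439 | 28% | 8% |
| 0.5 | 2.398 | 63% | 30% |

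At d = 0 the rates are the nominal 5% and 0.6%.

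**Step 4: layouts of random difficulty.** If each layout's difficulty varies with SD τ (in the same units), the difference between two layouts has SD τ√2. Simulated false rejection at the unadjusted 5% level is 10%, 23%, 37% and 56% for τ = 0.1, 0.2, 0.3 and 0.5.

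**Step 5: does counterbalancing work?** Let 12 athletes take layout A then B, and 11 take B then A. Average the two sequence-group mean changes: the layout difference enters with opposite signs and cancels. In simulation with layout differences of 0.2, 0.5 and 1.0 SD, the false rejection rate at 5% was 0.048 to 0.052 and the mean bias about zero. The standard error, in SDs of change, is ½√(1/12 + 1/11) = 0.2087, against 1/√23 = 0.2085 for the plain paired test. The price is about 0.1% in precision and one degree of freedom.

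**The case against.** **Eye Metrix may not be an endpoint.** The SAP names Dynavision and Senaptec activities, and the protocol also records items purely for continuity, such as Brock string progression. A reader might infer that layout difficulty will certainly be counted as a training effect. The documents do not support that. They support only the conditional: Eye Metrix is one of the eight training tasks, it has a recorded score, and the SAP's list is open-ended and does not exclude it.

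**The layouts at the scored sessions are not stated.** A reader might also infer that baseline and final scores are known to come from two different layouts. The re-arrangement sentence belongs to the training tasks, and the evaluations lie outside the eight training weeks. A fixed evaluation layout is not ruled out. If first-week and last-week training scores are compared, which the wording of the second outcome suggests, different layouts are the natural reading, though still an inference.

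**The layouts may be equally hard.** If so, there is no bias. A long search across two boards also averages over positions to some extent, and nothing shows that 0.5 SD is realistic. This stands, but the plan has no means of checking it.

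**Re-arranging has a sound purpose.** A fixed board would let athletes memorise positions, which would itself look like improvement. This stands too, and it is why the remedy should not be to stop re-arranging.

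**Other time effects remain.** Practice, season and motivation are also confounded with time here. That limits what the fix achieves; it is no reason to leave in a bias that can be removed cheaply.

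**Conclusion.** The point holds conditionally. If the Eye Metrix score is tested under the SAP's second outcome, and baseline and final scores come from different shared layouts, no analysis of the data can separate layout difficulty from change over time.

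The size and direction of the bias are unknown. The rates in the table show how sensitive the test is to assumed shifts; they do not predict this trial's error. The unadjusted column is not the planned analysis, because the SAP commits to a multiplicity correction. The Bonferroni column is one assumed version of it: the rates are lower, but still well above nominal.

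The scope is one of eight training tasks. The Senaptec Sensory re-evaluation, the SAP's first outcome, does not use the board and is not affected.

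**What to change.** State in the SAP whether Eye Metrix is analysed and which sessions supply its baseline and final scores. If it is analysed:

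- Keep the weekly re-arrangement for the training weeks in between.
- Chart two layouts, A and B, for the scored baseline and final sessions. Assign about half the athletes to A then B and half to B then A (12 and 11).
- Record the layout used for each score.
- Include a sequence (layout) term in the analysis of change.

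If this is not wanted, declare the Eye Metrix score descriptive only.

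A single reference layout at both sessions would be simpler, but it brings back some memory of positions. The A/B scheme gives no athlete the same layout at both scored sessions.

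The cost is charting two layouts and resetting the board between athletes at the scored sessions. The loss of precision is negligible. The change removes layout bias only; an Eye Metrix gain would still carry the other time effects of an uncontrolled design.

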Use "Proactive 60 seconds, 4 digit" and "Reactive 60 seconds, 4 digit settings". Perform each setting twice and record the best score and average reaction time. Adjust the height of the board for the athlete to touch the top and bottom buttons comfortably. Explain they are hitting as many of the red

lights, as quickly as possible once they light up, use GLOVE HAND ONLY. Use your peripheral vision to detect the lights, there will be a central stimulus of 4 digits you must verbally call out as they appear.

Explain the two modes; Reactive the lights will disappear if you are not quick enough. Proactive the lights will stay lit until you tap and deactivate it.

-SVT Go No Go

Use the setting “Research Softball Go-No go”. Repeat it twice, record their best score. Adjust the height of the board if needed. The participants must touch/deactivate the lights as quickly and accurately as possible using BOTH HANDS. They must recognize and decide to react or not react based on the colors given to them for Go, and No Go. Go will be yellow, like a softball. Brown will be No Go. The stimulus interval can be decreased by 50um intervals if the participants are achieving over 75% accuracy of Go. The interval cannot be increased to make it easier. Record % Go, % No Go and Time Interval.

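### SVT Go No Go: the interval may be shortened during training and is not reset for scored runs, so % Go before and after training can be measured at different difficulties

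*Protocol*

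**What the plan says.** The SVT Go No Go entry in the protocol's task descriptions sets a one-way progression rule. "The stimulus interval can be decreased by 50um intervals if the participants are achieving over 75% accuracy of Go", and "The interval cannot be increased to make it easier". Staff are told "Repeat it twice, record their best score" and "Record % Go, % No Go and Time Interval". The starting interval is not written there; it sits inside a named device setting. The opening section of the protocol gives a general permission, "Most of the activity's difficulty can be adjusted to be MORE difficult for progression", without exempting runs that will be scored. It also describes the eight training weeks as "not including the pre-evaluation and post evaluations, wash out and final evaluation", but neither document says whether SVT is run at those evaluations or at what setting.

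The SAP's second main outcome is "a comparison of baseline training performance to post training performance in sports vision training activities, such as Dynavision and Senaptec Sensory Trainer activities". For the analysis it states: "To analyze change in training performance, a student's T-test will be utilized to measure effect size and look for statistical significance". It does not name SVT, does not say which of the three recorded SVT quantities would be tested, and does not mention the interval.

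**The concern.** Go accuracy above 75% is what permits the harder task. The athletes who do well are therefore the ones whose last % Go may come from a shorter interval than their first. This happens when staff follow the protocol exactly; no deviation is needed. A before-after difference in % Go then mixes change in skill with change in difficulty. The protocol itself treats a longer interval as easier, so the mixing works against showing improvement in % Go. The direction for % No Go cannot be read from the documents.

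The obvious alternative, testing the recorded interval, has the opposite lean. The interval can stay or fall but cannot end above where it began, and an athlete already above 75% in week 1 qualifies for a step without having learned anything. The SVT result could thus lean either way, depending on a choice that the SAP leaves open.

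**Working it through.** The plan gives no sample size calculation, effect size, SD or numerical significance level for this task, so there is no planned figure to reproduce. The check is mainly one of logic.

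**Inputs.** From the protocol: 23 athletes, eight weekly sessions, the 75% threshold, shortening only, and three quantities recorded. From the SAP: baseline against post-training, t-test, an open list of activities, and a multiplicity correction of unstated form.

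**1. % Go as the tested quantity.** Write G(time, interval) for an athlete's % Go, with i0 the starting interval and i1 the interval at her final run. Then

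G(final, i1) − G(baseline, i0) = [G(final, i0) − G(baseline, i0)] + [G(final, i1) − G(final, i0)].

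The first bracket is the change in skill at a fixed difficulty. The second is the effect of the harder setting: zero if i1 = i0, and expected to be negative if i1 is shorter than i0.

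If k of the 23 athletes have progressed and the harder setting costs them d percentage points on average, the team mean change is understated by (k/23) × d:

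- k = 0: no bias
- k = 4: 4/23 = 0.17 d
- k = 7: 7/23 = 0.30 d
- k = 23: the full d

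The documents give neither k nor d, so this shows the form of the bias and not its size. The room for drift is also only a bound: if one step were taken between each pair of consecutive sessions, there would be at most 8 − 1 = 7 steps from week 1 to week 8.

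**2. The interval as the tested quantity (illustration only).** No document proposes this test. Code the change as 1 for k athletes who end one step shorter and 0 for the other 23 − k. The mean is k/23 and the sample variance is k(23 − k)/(23 × 22), so

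t = √[22k/(23 − k)], with 22 degrees of freedom.

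The step size and its unit cancel. At an unadjusted two-sided 0.05:

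| k | t | p |
|---|---|---|
| 3 | √(66/20) = 1.82 | 0.083 |
| 4 | √(88/19) = 2.15 | 0.043 |
| 5 | √(110/18) = 2.47 | 0.022 |
| 6 | √(132/17) = 2.79 | 0.011 |
| 7 | √(154/16) = 3.10 | 0.005 |

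The SAP promises a multiplicity correction. If that were Bonferroni over two tests (0.05/2 = 0.025), k = 5 would be needed; over eight (0.05/8 = 0.00625), k = 7. Both are assumptions. The table shows only that a quantity free to move in one direction can reach significance when few athletes move.

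**3. A reset.** The SVT entry, the protocol's general rules and the SAP contain no statement that scored runs return to the starting interval, and none that adjusts % Go for the interval.

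**The case against.** **SVT may not be affected at all.** The SAP's examples are Dynavision and the Senaptec trainer, and the protocol mentions evaluations outside the training weeks. If SVT is not analysed, or is scored at those evaluations at the base setting, the problem does not arise. This stands as a condition on the point. It does not remove it, because the list is open, SVT scores are recorded by instruction, and the SAP speaks of baseline performance in training activities.

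**The interval is recorded.** A reader might infer that the data are beyond repair. They are not: the mismatch can be seen, and % Go could be reported beside the interval or adjusted for it. But the SAP specifies none of this, and a choice made after seeing the data is what an SAP should prevent.

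**The rule against lengthening may be narrower than it looks.** The protocol's opening section bars making tasks easier than the base protocol, and the General Coaching Guidelines ask staff to avoid tasks so hard that nothing can be accomplished. Read together, a return to the starting interval may already be allowed. That is a fair reading, but on either reading no reset is provided for scored runs. On the strict reading, a reset needs an explicit exception.

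**The bias in % Go is conservative.** True: the harder setting can hide improvement in % Go but not create it. A lean towards a positive result arises only if the interval itself is tested.

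**Other tasks.** A reader might extend the point to the whole of the second outcome. The documents do not support that: Dynavision, Near Far Shift and Spatial Memory use named settings that probably already fix the difficulty. Nor does the protocol say when within a session an SVT step is applied, so it cannot be asserted that the two runs behind a best score differ in interval.

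**Conclusion.** The point holds as a conditional one, and acting on it is optional. If SVT is part of the second main outcome and is scored from training sessions, following the protocol can compare an easier baseline with a harder final run. A t-test on % Go then tends to understate improvement in the athletes who progressed. This rests on the protocol's own premise that a shorter interval is harder, and on staff using a step that is permitted but not required.

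The size is unknown. The bias is (k/23) × d, with neither term available. The p-values for an interval test illustrate a one-way measure at an unadjusted 0.05. A reader might take them as a false-positive rate for this trial, but the documents do not propose that test and do commit to a multiplicity correction.

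**What to change.** Two changes, limited to SVT.

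1. **Protocol, SVT Go No Go entry.** Write down the starting interval. State that the baseline and the post-training or final scored runs are done at that interval, as an explicit exception to the rule against lengthening, and that progressed intervals are for training only.
2. **SAP.** State whether SVT is in the second outcome. If it is, compare % Go and % No Go at the starting interval, and report the interval reached in training descriptively.

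**Cost.** About a sentence in each document. The existing scored runs are simply done at the starting interval, so none is added. A progressed training run afterwards would have to fit in the 45 − 38 = 7 minutes between the walk-through time and the session length. If training has begun, week 1 runs recorded at the starting interval can serve as baseline and only the final session changes.

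**Drawback.** Athletes well above 75% at baseline may reach a ceiling at the starting interval. If baseline has not yet been taken, one shorter common interval can be fixed for both time points; after baseline that option is gone. How training itself progresses stays with the sponsor.
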